9.4.4 Supportive analyses

Not applicable

9.5 Analysis of secondary variables

9.5.1 Efficacy variables

Maintenance of response

Maintenance of response will be defined analogously as in the primary endpoint in CAIN457A2304, but for week 104 and 156, i.e. PASI 75 response

- at Weeks 104 and 156, for subjects in the fixed interval regimens, or
- at Weeks 92 and 144, for subjects in the retreatment at start of relapse regimen who do not require active treatment at Week 92 or 144, respectively, or
- at Weeks 104 and 156, for subjects in the retreatment at start of relapse regimen who do require active treatment at Week 92 or 144, respectively.

Summary statistics for maintenance of response at Week 104 and 156 will be presented in contingency tables and will include absolute and relative frequencies. Confidence intervals for response rates will be derived as well based on the score method including continuity correction ([Newcombe 1998](#)).

PASI 50, PASI 75, PASI 90, PASI 100 and IGA 0 or 1 response over time

Summary statistics for PASI 50, PASI 75, PASI 90, PASI 100 and IGA 0 or 1 response by visit will be presented in contingency tables and will include absolute and relative frequencies. Confidence intervals for response rates will be derived as well based on the score method including continuity correction ([Newcombe, 1998](#)).

PASI score over time

Summary statistics will be provided for absolute PASI scores as well as for percent change from baseline by visit and treatment group. Figures will also be provided.

IGA mod 2011 score over time

Summary statistics for the IGA mod 2011 score over time will be presented by visit and treatment group in contingency tables.

Relapse

The number and percentage of subjects experiencing relapse will be presented by visit and treatment group.

Rebound

Rebound is defined as a worsening of PASI of > 125% of the value at baseline (core study), or new pustular, erythrodermic or more inflammatory psoriasis occurring within 8 weeks of stopping therapy (i.e., if this definition is fulfilled at more than 8 weeks after last study treatment administration, this is not defined as rebound). The number and percentage of subjects experiencing rebound will be presented by visit and treatment group.

9.5.2 Safety variables

All safety evaluations will be performed on the Safety set.

Adverse events

Treatment emergent adverse events are defined as any events started after the first dose of study treatment and within 84 days after the last study treatment, or events present prior to the first dose of study treatment, but increased in severity based on preferred term within 84 days after the last study treatment.

With the exception of adverse events that qualify as "treatment emergent" (see definition above), data collected from telephone visits and unscheduled visits in follow-up period 2 will only be included in individual patient listings, but not in summary tables.

AEs will be summarized by presenting, for each treatment group, the number and percentage of subjects having any AE, having an AE in each primary system organ class and having each individual AE (preferred term). Summaries will also be presented for AEs by severity and for study treatment related AEs. If a subject reported more than one adverse event with the same preferred term, the adverse event with the greatest severity will be presented. If a subject reported more than one adverse event within the same primary system organ class, the subject will be counted only once with the greatest severity at the system organ class level, where applicable.

Confidence intervals for relative frequencies will be derived as well according to the score method including continuity correction by [Newcombe, 1998](#).

Separate summaries will be provided for death, serious adverse event, other significant adverse events leading to discontinuation and adverse events leading to dose adjustment (including study treatment discontinuation).

A graphical display of relative frequencies within system organ classes and relative risks, if appropriate, will be presented.

For infections, time-to-event analysis will be done. Results will be tabulated and the Kaplan-Meier estimates for the cumulative rate will be plotted.

Additional analyses will be provided for adjudicated adverse events.

In supplementary analyses, exposure (or observation)-time adjusted analyses in terms of incidence rate and event rate will be provided.

Laboratory data

The summary of laboratory evaluations will be presented for three groups of laboratory tests (hematology, serum chemistry and urinalysis). Descriptive summary statistics for the change from baseline to each study visit will be presented. These descriptive summaries will be presented by test group, laboratory test and treatment group. Change from baseline will only be summarized for subjects with both baseline and post baseline.

For each parameter, the maximum change from baseline within each study period will be analyzed analogously.

In addition, shift tables will be provided for all parameters to compare a subject's baseline laboratory evaluation relative to the visit's observed value. For the shift tables, the normal laboratory ranges will be used to evaluate whether a particular laboratory test value was normal, low, or high for each visit value relative to whether or not the baseline value was normal, low, or high. These summaries will be presented by laboratory test and treatment group for the most extreme laboratory value post-baseline.

Immunogenicity

Summary statistics for baseline, each post-baseline visit and change from baseline to each visit will be provided. Summary statistics will be provided for the percent of subjects with immunogenicity. If appropriate, shift tables will also be presented.

Vital signs

Analysis of the vital sign measurements using summary statistics for the change from baseline for each post-baseline visit will be performed. These descriptive summaries will be presented by vital sign and treatment group. Change from baseline will only be summarized for subjects with both baseline and post-baseline values.

ECG

Summary statistics will be presented for ECG variables by visit and treatment group.

9.5.3 Resource utilization

Not applicable

9.5.4 Health-related Quality of Life

Summaries will be based on the FAS and will be presented separately for study periods (i.e., treatment period and follow-up period) if not specified otherwise.

EQ-5D

The EQ-5D is a questionnaire with 5 questions (regarding mobility, self-care, usual activities, pain/discomfort, and anxiety/depression) each with three categories (no problem, moderate problem, severe problems) and a health state assessment from 0 (worst possible health state) to 100 (best possible health state). The number and percentage of subjects in each of the three categories for each question will be presented by visit and treatment group. Summary statistics will be shown for the health state assessment by visit and treatment group.

DLQI[®]

The DLQI measures functional disability of subjects with dermatological disorders that are greater than 18 years of age and had been utilized as a relevant clinical measure in atopic dermatitis, as well as other dermatitis clinical trials. The DLQI is a simple, validated, self-administered 10-item questionnaire. The instrument contains six functional scales (i.e., symptoms and feeling, daily activities, leisure, work and school, personal relationships, treatment). For the DLQI, each question will be answered with the following response: "not at all," "a little," "a lot," or "very much". Seven scores will be derived from the DLQI: the total score of each of the six dimensions as well as the total score over all items. The higher the score, the more quality of life is impaired.

For each of the seven scores the percentage change from baseline will be derived. Summary statistics will be provided for absolute values as well as for the percentage change by visit and treatment group.

In addition, summary statistics will be provided for number of subjects achieving DLQI 0 or 1.

HAQ[®]-DI (for subjects with PsA at baseline of the core study)

Summary statistics will be derived for HAQ[®]-DI score over time for all subjects with psoriatic arthritis recorded on the Psoriatic Arthritis History eCRF at screening visit of the core study. Absolute and relative frequencies for HAQ[®]-DI response will also be presented. HAQ[®]-DI response is defined by an improvement of 0.3 score points compared to baseline.

9.5.5 Pharmacokinetics

All completed subjects with quantifiable PK measurements of secukinumab will be included in the PK data analysis. Serum concentrations will be expressed in mass per volume units. All concentrations below the limit of quantification or missing data will be labeled as such in the concentration data listings. PK concentrations will be summarized by visit and treatment group. In addition to mean, standard deviation, coefficient of variation, median and quartiles, the geometric mean and geometric coefficient of variation and n(log) will be presented.

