5.2 Treatment arms

Subjects will continue in the treatment arm that they were assigned to during the CAIN457A2304 core study or the CAIN457A2307 core study until Week 156. At Week 156, subjects who rolled over from the CAIN457A2304 core study will be unblinded and may switch to one of the treatment options described below according to investigator judgment; subjects who rolled over from the CAIN457A2307 core study will continue being treated with secukinumab 300 mg s.c. every four weeks. Treatment arms in this study may be affected by agency review or potential product approval considerations, whereby if the product is approved during study conduct, dose groups in this proposed extension trial may be amended (via a future protocol amendment) based on eventual agency recommendations for product usage in this indication.

The study treatment will be provided in individual boxes that contain secukinumab or placebo PFS sealed in a plastic wrapper. Each study treatment box consists of actual PFS and a safety device type X100L [REDACTED]. The safety syringe is provided with a needle guard system that will aid protection from accidental needle sticks.

Double-blind treatment arms for subjects entering from the CAIN457A2304 core study

During the core study CAIN457A2304, within each treatment regimen, subjects were assigned to either the 150 or 300 mg s.c. secukinumab in PFS, thus resulting in four treatment arms overall which will be maintained until Week 156:

Fixed-time interval regimen – “FI”: either 150 or 300 mg s.c. secukinumab in PFS: In the treatment period subjects will receive the same dose they received during the maintenance period of the CAIN457A2304 core study. Thus, secukinumab 150 mg subjects will continue to

receive 150 mg secukinumab every four weeks, and secukinumab 300 mg subjects will continue to receive 300 mg secukinumab every four weeks, from Week 52 up to and including Week 152.

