Retreatment at start of relapse regimen – “SoR” “start of relapse”: either 150 or 300 mg s.c. secukinumab in PFS: “Start of relapse” will be defined as a loss of $\geq 20\%$ of the maximum PASI gain achieved during the CAIN457A2304 or CAIN457A2304E1 study, compared to baseline of the CAIN457A2304 study, *and* a loss of PASI 75 response. Whenever a subject fulfills the start of relapse criteria, active secukinumab will be administered at their scheduled visits (i.e., every four weeks) until the subject is back to PASI 75 response, at which point in time they will start receiving placebo again. The dose administered in the treatment period of this extension study (secukinumab 150 mg or 300 mg in PFS) will be identical to the dose that these subjects received during the maintenance period of the CAIN457A2304 core study. If a subject does not fulfill the criteria of a start of relapse or is back to PASI 75 response after a start of relapse, they will receive placebo PFS injections (two injections per dose) to maintain the blind. This treatment regimen is applied every four weeks, from Week 52 up to and including Week 152.

At Week 156, patients from the maintenance period of the CAIN457A2304 core study will be unblinded and continue in the study on one of the treatment options in [Table 5-1](#) according to investigator judgment for their assigned treatment arm.

Table 5-1 Open-label treatment options starting at Week 156

Previous treatment arm through Week 152 (Unblinded at Week 156)	Treatment options, as decided by the investigator	New office visit frequency
Secukinumab 300 mg FI	Continue secukinumab 300 mg FI	Every 12-16 weeks
Secukinumab 300 mg SoR	Continue secukinumab 300 mg SoR for remainder of the study OR Switch to secukinumab 300 mg dosed every 4 weeks	Every 4 weeks Every 12-16 weeks
Secukinumab 150 mg FI	Continue secukinumab 150 mg FI OR Switch to secukinumab 300 mg dosed every 4 weeks	Every 12-16 weeks Every 12-16 weeks
Secukinumab 150 mg SoR	Continue secukinumab 150 mg SoR for remainder of the study OR Switch to secukinumab 300 mg dosed every 4 weeks	Every 4 weeks Every 12-16 weeks

Open-label treatment arm for subjects entering from the CAIN457A2307 core study

Secukinumab 300 mg s.c. in PFS regimen arm: Each subject to continue receiving two s.c. injections of 150 mg secukinumab in PFS every four weeks. Doses will be administered from Week 52 up to and including Week 256.

Overview of treatment schedule according to treatment arm

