For subjects willing to self-inject, the first use at enrollment visit (Week 52) will take place under guidance and the supervision of one site staff member. At the enrollment visit (Week 52) the site staff will walk subjects through the “Instructions For Use” on how to self-inject via PFS. At the following visits, subjects will receive the PFS and instructions at the study site to follow on their own.

NOTE: The needle cover of the syringe contains dry rubber (latex), which should not be handled by persons sensitive to this substance.

During the treatment period from Week 52 until Week 256, subjects will receive a maximum of 104 study treatment injections (2 injections of secukinumab 150 mg PFS and/or placebo PFS at each visit). The actual number of study treatment injections will depend on the treatment assigned. All subjects will receive 52 study treatment injections between Week 52 and Week 152 (2 injections of secukinumab 150 mg PFS and/or placebo PFS at each visit); between Week 156 and 256 subjects could receive as many as 52 study treatment injections (2 injections of secukinumab 150 mg PFS every four weeks) or as few as 0 study treatment injections (SoR treated subjects who do not meet start of relapse criteria at any point).

At study visits when pre-dose blood samples have to be drawn ([Table 6-1](#)), the study treatment will be injected to the subject only after the blood samples have been taken.

At each visit, all study assessments, including the completion of Patient Reported Outcomes (PROs), should be completed prior to the self injection of study treatment.

After Week 256, no further study treatment will be administered during the treatment period. In addition, no study treatment is administered during the follow-up period and follow-up 2 period.

The subject should be instructed to contact the investigator if he/she is unable for any reason to attend a study visit as scheduled.

All dates, times of injections, mode of injection (self or by study site staff) during the study must be recorded on the Dosage Administration Record eCRF. Immediately before dispensing the package for injection, investigator staff will detach the outer part of the label from the packaging and affix it to the source document (Drug Label Form) for that subject's unique subject number.

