5.5.11 Study completion and post-study treatment

- A subject entering into CAIN457A2304E1 will be said to have completed the extension study after he/she has completed all visits and assessments as defined in [Table 6-1](#) and received all doses of the study treatment in accordance with the protocol.
- The extension study as a whole will be considered complete when all eligible subjects rolled over from the core study (e.g., CAIN457A2304 or CAIN457A2307) have completed as per protocol the visits and assessments defined in [Table 6-1](#) for study CAIN457A2304E1.

The investigator also must provide follow-up medical care for all subjects who are prematurely withdrawn from the study, or must refer them for appropriate ongoing care. Subjects who complete CAIN457A2304E1 may be eligible to enter another planned extension trial.

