An ELISA method will be used for bioanalytical analysis of AIN457 in serum, with an anticipated lower limit of quantification (LLOQ) of 80 ng/mL. The detailed method description to assess AIN457 concentration will be described in the bioanalytical raw data of the study and in the respective BDR.

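### The PK analysis keeps only completers with quantifiable levels, which discards valid samples and can bias the start-of-relapse summaries upward

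*Protocol*

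**What the plan says.** Protocol 9.5.5 sets the inclusion rule: "All completed subjects with quantifiable PK measurements of secukinumab will be included in the PK data analysis". Concentrations are then summarized by visit and treatment group with arithmetic statistics, median and quartiles. In addition, "the geometric mean and geometric coefficient of variation and n(log) will be presented". The only rule for low values concerns listings: "All concentrations below the limit of quantification or missing data will be labeled as such in the concentration data listings". Protocol 6.6.4 describes the assay, "with an anticipated lower limit of quantification (LLOQ) of 80 ng/mL".

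Section 9.5.5 does not define a completer. The nearest definition is in Protocol 5.5.11, where a subject "will be said to have completed the extension study after he/she has completed all visits and assessments" in Table 6-1 and received every dose as the protocol requires.

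The arms differ in how often active drug is given. Fixed-interval (FI) and open-label subjects are dosed every four weeks. Under Protocol 5.2, SoR subjects up to Week 152 who are not in relapse, or who have regained PASI 75, are handled differently: "they will receive placebo PFS injections (two injections per dose) to maintain the blind". Those who stay on SoR after Week 156 get nothing outside relapse (Table 5-3). Protocol 5.5.4 allows for "as few as 0 study treatment injections (SoR treated subjects who do not meet start of relapse criteria at any point" between Weeks 156 and 256.

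The SAP follows Protocol Section 9 (SAP 1). It has no PK section, no PK row in Table 1-2, and no PK entry among the changes in 1.1.1. Its rule for values below quantification (SAP 1.4.2 and 1.9.2) covers laboratory tests only.

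**The concern.** Both entry conditions depend on what happens after enrollment, and one of them depends on the regimen itself.

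Requiring completion throws away data the protocol asked for. A subject who stops at Week 140 has given PK samples at Weeks 64 to 128, and should also have the Week 260 assessments, which include a PK draw, about four weeks after the last dose. Under the rule none of these samples is used.

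Requiring a quantifiable level removes a SoR subject whose every level is below 80 ng/mL. That is a valid measurement, and the absence of drug is what the regimen intends for someone who has not relapsed.

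The missing BLQ rule is a further problem. One programmer could drop BLQ values from the visit means and another could set them to 0, and both would be following the plan. At stake is whether the PK tables describe exposure in everyone treated on a regimen, or only in a selected part of them.

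**Working it through.** Neither document gives a PK concentration, a BLQ rate or a PK result, so there is no figure to reproduce. The checks below use the document figures that exist and assumed ranges for the rest.

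**1. Restriction to completers**

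- Input: about 108 of 675 subjects had discontinued (Protocol, Amendment 1 rationale), so d = 108/675 = 0.16. Later discontinuations would add to this.
- Assumption: r is the mean level in discontinuers divided by that in completers, taken over 0.5 to 1.5.
- Completer mean / all-subject mean = 1/(1 - d + d·r).
- r = 0.5: 1/(0.84 + 0.08) = 1.087.
- r = 1: 1.00.
- r = 1.5: 1/(0.84 + 0.24) = 0.926.

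The direction depends entirely on r, which the documents do not give.

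**2. Exclusion of subjects with no quantifiable level**

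- Let a be the share of an arm with no quantifiable sample. With those subjects counted as 0, the mean without them is 1/(1 - a) times the mean with them.
- Assumed a = 0.2%: 1.00. a = 10%: 1.11. a = 20%: 1.25.
- Table 15-1 lists nine extension samples (Weeks 64, 76, 104, 116, 128, 156, 208, 260 and 268; the Week 52 sample belongs to the core study). If each had the same BLQ probability f and visits were independent, a = f^9: 0.5^9 = 0.2% and 0.75^9 = 7.5%.
- Independence is the favorable case. A subject who stays off drug tends to be BLQ repeatedly, and with full correlation a rises to f itself.

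This component can only raise the arithmetic mean. The dosing rules place it mainly in the SoR arms.

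**3. BLQ samples of included subjects, if they are dropped**

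- With M the mean of the quantifiable samples and b the value given to a BLQ sample, the ratio of the quantifiable-only mean to the all-sample mean is M/((1 - f)M + f·b).
- For b = 0 this is 1/(1 - f). At f = 20%: 1/0.80 = 1.25. At f = 50%: 1/0.50 = 2.0.
- For b = 80 ng/mL, f = 50% and assumed M of 500 to 20,000 ng/mL: 500/(250 + 40) = 1.72, up to 20,000/(10,000 + 40) = 1.99.
- For an assumed f of 1% to 5%, as might apply under dosing every four weeks: 1.01 to 1.05.

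These factors apply to the arithmetic mean only, not to the median, quartiles or geometric mean.

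**The case against.** The strongest reply is that Section 9.5.5 selects subjects, not samples. A SoR subject with one quantifiable level qualifies, and nothing says that the subject's BLQ samples at other visits are dropped. The request for a separate n(log) is most useful when some summarized values, such as zeros, cannot be logged. That hints that BLQ values may enter arithmetic means as 0. This stands: step 3 is conditional, and only step 2 follows from the inclusion rule itself. It does not remove the gap, because n(log) is a hint and not a rule. Even with zeros kept, the geometric mean would rest on quantifiable values alone.

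A reader might infer that the completer restriction also pushes levels up, because subjects who lose efficacy may have low concentrations. The documents do not support this. Under Protocol 5.5.9 subjects also stop for adverse events, laboratory findings, pregnancy or withdrawn consent. SoR completers could equally be those who needed less active drug.

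A reader might also infer that an FI versus SoR exposure comparison is understated. No such comparison is planned. The PK output is descriptive, PK/PD is marked not applicable (Protocol 9.5.8), the SAP does no formal testing (1.8.3), and PK is not a primary or secondary objective.

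Finally, setting BLQ to 0 is only one convention; the SAP sets laboratory values below quantification to the limit itself. That also stands, so the case for change rests on the inclusion rule and the BLQ count rather than on any one substituted value.

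**Conclusion.** The point holds as a minor one. The rule discards valid samples from subjects who did not complete, with an effect of unknown direction: 0.93 to 1.09 times at 16% discontinued, over assumed level ratios of 1.5 to 0.5. It also excludes subjects with no quantifiable level. That can bias SoR means upward by 1/(1 - a), from about 1.00 at an assumed 0.2% to 1.25 at an assumed 20%. If BLQ samples of included subjects are dropped as well, which the text leaves open, arithmetic visit means are inflated by 1.25 times at an assumed 20% BLQ and 2.0 times at an assumed 50%, relative to counting them as 0.

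The conclusion takes the Protocol 5.5.11 meaning of completion. Every BLQ share, concentration and level ratio used is an assumption. Because the completer effect could run either way, an upward net bias in the SoR arms is possible but not demonstrated. Only the descriptive PK summaries are affected; the primary safety analysis does not depend on them.

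**What to change.** Replace the inclusion rule in Protocol 9.5.5, or override it in a short PK section of the SAP:

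- Include all treated subjects with at least one valid PK sample, whether or not they completed and whether or not any level is quantifiable.
- Report the number and percent BLQ by visit and treatment group.
- State one BLQ convention for arithmetic statistics, for example 0, with medians shown alongside.
- State that geometric statistics use only values that can be logged, with n(log) giving the count.

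The cost is a few sentences, a footnote on the logged values and a rerun of the PK tables. No new samples or data are needed.
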